3.2 Primary Study Endpoints

Primary Efficacy End Point: The primary end point is a mean reduction in corneal staining score after 8 weeks of treatment, as measured by Fluorescein and Lissamine dye staining.

Primary Tolerability End Point: The change in the test substance tolerance between Day 1 (post-dose) and at weeks 2, 4, 6 and 8.

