3.3 Secondary Study Endpoints

The secondary study endpoints will include:

- 1. The change in the Ocular Surface Disease Index (OSDI) which is a patient's subjective rating scale
- 2. Change in tear secretion as measured by Schirmer I test
- 3. The proportion of eyes achieving complete corneal staining clearance after treatment
- 4. Change in conjunctival surface staining score as measured by Fluorescein and Lissamine dye staining
- 5. The change in subjective ocular surface redness score (OR) using the validated bulbar redness (VBR) grading scale
- 6. Visual acuity change
- 7. Change in frequency of administration of artificial tears or concomitant eye drops
- 8. Change in number of corneal filaments (slit-lamp examination)
- 9. Change in amount of mucoid films (slit-lamp examination)
- 10. Clinical Global Impression (CGI) of change in symptoms from baseline (physician's rating)
- 11. Subject Global Assessment (SGA) of overall change from baseline (subject's rating)
- 12. Change in Non-Invasive Keratograph Tear Break-Up Time (NIKBUT)
- 13. Change in Tear Meniscus Height (TMH)
- 14. Change in Keratograph Ocular Bulbar Redness Score
- 15. Change in MMP-9 Protein Detection
- 16. Change in Tear Fluid Osmolarity
- 17. Change in eDNA abundance in tear fluid
- 18. Change in tear fluid cell count
- 19. Change in eDNA strand length on Schirmer test strip impressions

Corneal filaments are mucous tags that are adherent to the surface of cornea. Mucoid films are mucous collections accumulating on the surface of the eye. The number of such mucus tags/ filaments will be counted on each clinical examination (slit-lamp examination).

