3.4 Safety Endpoints

Safety assessments include Vital Signs, recording of all complications and adverse events, as well as ophthalmic exam findings. All ocular and non-ocular adverse events will be assessed for severity and relationship to the investigational product.

Primary safety endpoint:

• The proportion of subjects at week 8 who were able to successfully complete a full eight weeks of therapy with topical administration four times per day (q.i.d.)

Secondary safety endpoint:

- All adverse events reported, whether deemed related to treatment, or not.
- Clinically significant changes in vital signs or ophthalmic examination from baseline.

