7.2 Statistical Methods

Biostatisticians from the Design and Analysis Core (DAC) of UIC-CCTS will perform the analysis. We will assess treatment efficacy based on the intent-to-treat principle using each participant's randomized treatment assignment to define treatment groups and outcomes. Safety variables will be analyzed with regard to treatment that participants actually received (the safety population). One eye (target eye) will be selected at screening visit for statistical comparisons as follows: (i) if only 1 eye meets inclusion criteria, this eye is used; (ii) if both eyes meet inclusion criteria, the eye with the higher RBS score is used; (iii) if both eyes have the same RBS score, then the one with the lower Schirmer I score is used; (iv) if both eyes have same scores, the right eye is used. Secondary analyses will be performed for the non-target eye as well. To assess the effect of treatment, we will compare each outcome measure between rhDNase I (study) vs. Vehicle (control) group over time using general linear mixed model, mixed-effects ordinal logistic regression, and mixed-effects multinomial logistic regression for continuous, ordinal and nominal variables respectively. Treatment, time and their interaction will be included in the model. Missing values of less than 25% will be imputed by using multiple imputations; otherwise will not be included in the analysis. Descriptive statistics will be utilized before the modeling to describe the sample. Assumptions behind each statistical method will be examined. Two-sided Pvalue less than 0.05 would be considered as statistical significance. All the analyses will be conducted by using SAS 9.2 (SAS Inst., Cary, NC).

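### Section 7.2 labels any two-sided P<0.05 as statistical significance for all 22 named endpoints and the repeat analyses in the second eye, so significant results outside the primary efficacy test cannot be told from chance

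*Combined protocol and SAP*

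**What the plan says.** Section 7.2 states "we will compare each outcome measure between rhDNase I (study) vs. Vehicle (control) group over time", and for the models "Treatment, time and their interaction will be included in the model". It then sets a single criterion, "Two-sided Pvalue less than 0.05 would be considered as statistical significance", and adds "Secondary analyses will be performed for the non-target eye as well". The synopsis carries the same rule.

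The rule applies to these endpoints:

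- **Primary efficacy (3.2):** reduction in corneal staining "after 8 weeks of treatment, as measured by Fluorescein and Lissamine dye staining".
- **Primary tolerability (3.2):** "The change in the test substance tolerance between Day 1 (post-dose) and at weeks 2, 4, 6 and 8".
- **Primary safety (3.4):** "The proportion of subjects at week 8 who were able to successfully complete a full eight weeks of therapy".
- **Secondary (3.3):** a numbered list that ends at "19. Change in eDNA strand length on Schirmer test strip impressions".

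Section 7.1 sizes the trial on corneal staining alone. No section gives a testing order across endpoints, a split of alpha, an adjustment, or a statement that secondary results are nominal or exploratory.

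**The concern.** A rule that calls every P<0.05 statistically significant, applied to a long list of endpoints, produces significant results from an inert drug with a probability well above 5%. The objective is preliminary efficacy, so the secondary results are likely to be used to argue for further development. As the plan is written, a report could follow it exactly and present one significant secondary endpoint in the same terms as the primary. A reader could not tell that result from chance.

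**Working it through.** **Inputs.** Two-sided alpha 0.05 per test (7.2). Three endpoints labelled primary (3.2, 3.4) and 19 secondary (3.3), so 22. One test per endpoint. The protocol gives no correlations between endpoints, so a common correlation of 0, 0.3 or 0.5 is assumed throughout. All figures suppose no true effect on any endpoint.

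**The plan's own figure first.** The protocol states no familywise error rate; its only related figure is the sample size in 7.1. The difference is 3.1 − 1.24 = 1.86 and the SD is 2.5, a standardised effect of 1.86/2.5 = 0.744. A two-sided two-sample t test at alpha 0.05 and 80% power needs 29.35, so 30 per group, which reproduces the plan. Power at the 36 per group to be enrolled is 87.6%.

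**Expected false positives.** 19 × 0.05 = 0.95 among the secondaries, in either direction. In the favourable direction, 19 × 0.025 = 0.475, about 0.5. These do not depend on the correlation.

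**At least one false positive, independent tests.**

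- 19 secondaries, either direction: 1 − 0.95^19 = 62.3%.
- All 22, either direction: 1 − 0.95^22 = 67.6%.
- 19 secondaries, favourable direction: 1 − 0.975^19 = 38.2%.
- All 22, favourable direction: 1 − 0.975^22 = 42.7%.

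**Correlated tests.** With equicorrelated normal statistics, write each as √ρ·U + √(1−ρ)·e, with U shared and e independent. The chance is 1 minus the integral over U of the conditional probability of no rejection, raised to the number of tests. For the favourable direction all endpoints are oriented so that positive means benefit.

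| Tests | Direction | ρ = 0 | ρ = 0.3 | ρ = 0.5 |
|---|---|---|---|---|
| 19 | either | 62.3% | 52.5% | 40.9% |
| 22 | either | 67.6% | 56.9% | 43.9% |
| 19 | favourable | 38.2% | 27.2% | 20.5% |
| 22 | favourable | 42.7% | 29.6% | 22.1% |

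The either-direction chance drops below 50% at a common correlation of about 0.35 for 19 tests and about 0.41 for 22.

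**What the count leaves out.** One test per endpoint is a low count. The Subject Global Assessment has two questions (3.3.4), the Keratograph gives two break-up times (3.3.6), and redness is graded nasally and temporally (3.3.5). The second eye adds tests only for per-eye outcomes. If 16 of the 22 are taken as per eye (an assumption from the visit schedule), the total is 22 + 16 = 38. With endpoint correlation from 0 to 0.7 and between-eye correlation from 0.5 to 0.8, simulation gives a 41% to 84% chance of at least one false positive in either direction.

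**The case against.** The strongest reply is that this is a single-centre Phase I/II trial whose efficacy aim is called preliminary. It names one primary efficacy endpoint, labels the rest of the efficacy list secondary, and is sized on that one endpoint at alpha 0.05. The 5% error of that test is intact. The tolerability and safety endpoints answer separate questions, and nothing says that success on any one of the three is trial success, so pooling the primaries into one error rate is not called for. All of this stands. It does not limit the rule in 7.2, which attaches the word significance to every outcome measure.

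Two stronger readings are tempting, and the documents do not support them.

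- **That a false positive finding is more likely than not.** This needs no effect on any endpoint, rejections counted in both directions and, with one test per endpoint, a fairly low common correlation. Several listed endpoints overlap: two bulbar redness scores, physician and subject global ratings, two eDNA measures, and complete corneal clearance, which derives from the primary score. Independence is therefore the least plausible case. For claims of benefit the chance is below 50% even under independence.
- **That each endpoint is tested at several visits and in two sets of eyes.** Section 7.2 describes one model per outcome and states no visit-by-visit tests, although it does not name the deciding contrast. Staining, Schirmer and the tear-fluid assays have only Week 8 after baseline, and acuity only Week 10. The OSDI, the two global ratings and the tolerance scale are per subject.

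**Conclusion.** The concern holds in this form: the single P<0.05 rule, followed as written, makes significant results outside the primary efficacy test uninterpretable. Under no effect on any endpoint and one test per endpoint, at least one of the 19 secondaries would be called significant with probability of about 41% to 62%, or about 21% to 38% counting favourable results only, for common correlations from 0.5 down to 0. Those correlations are assumptions; higher values lower the figures (28.3% for 19 tests, either direction, at 0.7), but they remain far above 5%.

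The primary efficacy test is not invalidated. This leaves aside the interim efficacy reviews that section 9.4.1 allows, which are a separate matter. The point deserves correction before unblinding, because a hierarchy chosen after the results are seen would not be credible.

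**What to change.** In section 7.2 and the synopsis, replace the single criterion with text to this effect:

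- Significance at two-sided 0.05 is claimed only for the between-group difference in Week 8 corneal staining in the target eye.
- The tolerability and safety endpoints are reported as estimates with 95% confidence intervals. Align their primary labels in 3.2 and 3.4 with this.
- The 19 secondary endpoints and all non-target-eye analyses are reported with an estimate, 95% confidence interval and nominal P value, without a claim of significance.

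A multiplicity correction across the 19 that runs whatever the primary shows is not advised. Two separate families at 0.05 allow up to 0.05 + 0.05 = 10% overall. Any formal secondary claim should be tested only after the primary succeeds.

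**Cost.** Fewer results may be called significant. The change is to protocol text, so it goes to the IRB (section 12) and to the DSMB as a proposed modification (9.4.1). No subjects, visits or procedures are added. Alpha for the primary stays at 0.05 and its power at about 88% with 36 per group, under the assumptions in 7.1.

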7.3 Subject Population(s) for Analysis

Subject population for analysis will include any subject enrolled in the study who received at least two weeks of treatment with study eye drops and attended at least the first post-treatment (week 2) follow up visit.

8 Safety and Adverse Events

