The most likely discomforts a subject may experience by using rhDNase I administered as eye drops are eye burning or irritation, red watery eyes, or feeling like there is something in the eye. To see how subjects react to the study medication, their first dose will be given by the investigator in the clinic itself. Afterwards subjects will be asked to rate tolerability of the drug on the Visual Analogue Scale. Also, at each visit, subjects will be asked to complete the Visual Analogue Scale.

An allergic reaction to the drug cannot be predicted beforehand. In event of an allergic reaction, the drug will be stopped immediately, and symptoms will be managed appropriately depending on the severity of the reaction.

No single agent has yet been approved by the FDA for GVHD prevention or therapy.³⁴ Contact lenses, commonly used to treat oGVHD, will be withheld during the 14 day wash-out period and over the entire course of the study. Stopping contact lens wear may increase the subject's risk of worsening oGVHD. All study subjects will be encouraged to contact the research team immediately if they experience worsening of oGVHD.

No psychological, social, legal, or financial risk is expected from participating in the research.

There is always a risk of a loss of confidentiality.

2 Study Objectives

The objective of this study is to establish whether patients with ocular graft-vs.-host disease (oGVHD) are able to tolerate receiving rhDNase I 0.1% eye drops four times a day for eight weeks (primary tolerability objective) and to investigate the preliminary efficacy of rhDNase I 0.1% topical eye drop solution in treating oGVHD (primary efficacy objective).

3 Study Design

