3.1 General Design

This will be a Randomized controlled trial, in which a total of 72 subjects will be enrolled at 1 clinical site. Subjects will be randomly assigned to one of two groups (#1, #2), with 36 subjects per group. One group will be given placebo (Vehicle eye drops) and the other group will be given eye drops containing the study drug (rhDNase I 0.1%).

Patients with established oGVHD will be approached by a member of the research staff to determine if he/ she might be interested in participating in a research study. If the subject is interested, the research staff member will describe the study. If the subject is willing to enter the study, the study will be discussed and the subject will be asked to sign the informed consent form. Consent will be obtained prior to screening to determine eligibility. Screening procedures include documentation of definite oGVHD. Eligible subjects will be enrolled in the study.

All enrolled subjects will receive their first dose of test medication (placebo/ study drug) on study Day 1 in the doctor's office, and after completion of the study assessments, will have the topical eye drops dispensed for self-administration. See Section 5.4 *Preparation and Administration of Study Drug* for details.

Subjects will be provided with diaries to record the time of each dose and will also be asked to record any adverse symptoms. In addition, they will be asked to make a note of any missed doses together with the reason for the omission. Subjects will return two weeks later on Day 14 for further study assessments, thereafter at 4 weeks, 6 weeks and 8 weeks (the last day of treatment), and again at 10 weeks after two weeks of no treatment with study drug for the final study assessments.

Because NETs have an important role in the innate defense against microbes,³⁵ treatment with DNase I to clear NETs may increase susceptibility to ocular surface infections. Symptom relief is an important goal in patients having dry eyes, with the proviso that treatment does not interfere with pathogen defense. Therefore, we will determine whether DNase I treatment affects the ocular surface microbiome.

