Subjects currently treating oGVHD with corticosteroids and/or Restasis will continue these treatments during the whole study. If patients are wearing contact lenses (Soft bandage contact lenses or PROSE lens), they will be asked to discontinue contact lens wear for 1 month prior to being enrolled (Baseline visit) and will be required to not wear contact lenses for the duration of the study (until week 10 visit). The study doctor will provide advice about decreasing oGVHD symptoms with artificial tears, eyelid massage, or warm compresses.

If the subject agrees to enter the study, the first treatment visit will be scheduled. If a washout period is needed, visit 2 will be after 2 weeks (±4 days). If a washout period is not necessary, visit 2 can be scheduled any time in the next 2 weeks after the screening visit.

6.5.2 Visit 2 Day 1 (Randomization and First treatment visit) Prior to first dose (Baseline)

- Vital Signs (blood pressure taken while subject is relaxed in a sitting position for at least 3 minutes, pulse, temperature, and height and weight (at this visit only).
- BSCVA (Snellen's chart)
- OSDI
- Schirmer 1 test and Fluorescein and Lissamine Dye staining
- Keratograph Oculus Redness Score
 - > Non-invasive Keratography Tear Film Break-up Time (NIKBUT)
 - > Tear Meniscus Height (TMH)
- TearLab Osmolarity Test
- InflammaDry Test for MMP-9 Protein
- Baseline Ophthalmic Examination (slit lamp examination, Ocular surface redness score)
- Tear fluid collection for analysis (PicoGreen, Cellometry)
- Physical Inspection of the Nose and Oropharynx
- Conjunctival and eyelid margin cultures
- Record changes in concomitant medication
- Adverse events since screening visit.

Randomization (by pharmacy)

Investigator/designee administers first dose

Post-Dose

RhDNase treatment for ocular GVHD Version: 10.0; 07-26-2018

Page 30 of 47

- Test Substance Tolerance (Visual Analogue Scale; VAS)
- Subjects will be trained on how to self-administer the study eye drops and be given a sufficient supply to last for 2 weeks to take home.
- Subjects will receive a study diary on which to record the day/time of each dose and any adverse effects.
- Post dose evaluation for any adverse effects.

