6.5.3 Visit 3: Week 2 (± 2 days)

Treatment Visit (after any dose for that day)

- Vital Signs
- OSDI
- Clinical Global Impression, Subject Global Assessment
- Test Substance Tolerance (VAS)
- Ophthalmic Examination (slit lamp examination, Ocular surface redness score)
- Physical Inspection of the Nose and Oropharynx
- Review the subject's diary and record changes in concomitant medication, deviations from drug schedule and adverse events.
- Subjects will be given study medication, sufficient to last for 2 weeks, to take home.

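### The only analysis population with a membership rule (7.3) depends on events after randomisation, contradicts intent-to-treat in 7.2, and leaves the denominator for eight-week completion unstated

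*Combined protocol and SAP*

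**What the plan says.** Section 7.2 sets two principles. For efficacy, "We will assess treatment efficacy based on the intent-to-treat principle", with groups formed by randomised assignment and no condition on exposure or attendance. For safety, "Safety variables will be analyzed with regard to treatment that participants actually received (the safety population"). The safety sentence says which arm a subject is counted in. It does not say who is counted.

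Section 7.3 then gives a single population: anyone enrolled who "received at least two weeks of treatment with study eye drops and attended at least the first post-treatment (week 2) follow up visit". It is not labelled as efficacy, safety, per-protocol or modified intent-to-treat. The statistical entry in the Study Summary mentions no analysis population.

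The primary safety endpoint in 3.4 is "The proportion of subjects at week 8 who were able to successfully complete a full eight weeks of therapy", on four-times-daily dosing. No denominator is given. The primary tolerability endpoint in 3.2 is the change in the tolerance VAS from Day 1 post-dose to weeks 2, 4, 6 and 8.

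Several other places bear on who has data:

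- Section 3.1: "All enrolled subjects will receive their first dose of test medication (placebo/ study drug) on study Day 1". Section 6.5.2 collects a VAS rating after that dose.
- Section 4.4.2 asks early withdrawers for the week-10 procedures and a further VAS rating.
- Section 5.7 withdraws from the study anyone whose study drug is discontinued.
- Section 8.1 allows subjects withdrawn for an adverse event to be replaced, without saying how they are then counted.
- Section 8.5.3 evaluates all exposed subjects for adverse events, but does not call them an analysis set or link them to completion.

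**The concern.** The first objective in section 2 is whether patients can tolerate the drops for eight weeks. Section 1.5 names burning and irritation as the likeliest discomforts and has the first dose given in the clinic to see how subjects react. Stopping in the first days because of discomfort is therefore a foreseeable way for treatment to fail. If 7.3 is the denominator, such a subject is removed because of the very outcome being measured. The completion rate is then overstated, and an early difference between arms largely drops out of it.

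The rule can also exclude someone seen within the week-2 window. The visit is set for Day 14 with two days either way (3.1, 6.5.3). A subject seen on Day 12 or 13 who stops there has attended, but has had fewer than 14 days of treatment.

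If instead the safety population of 7.2 is the denominator, the result depends on a membership rule not yet written. For efficacy, selecting on treatment received and attendance is not the comparison that 7.2 promises.

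Intolerance itself is not hidden: adverse events, the withdrawals they cause and reasons for dropout are still recorded (8.3, 8.4, 8.5.3, 9.5). The gap concerns the completion proportion, the VAS set and the efficacy set.

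**Working it through.** **The plan's own figure.** Section 7.1 assumes means of 3.1 and 1.24, SD 2.5, two-sided alpha 0.05 and 80% power. The difference is 3.1 − 1.24 = 1.86. The normal approximation gives 29 per group. The two-sample t test gives 29.35, hence 30, with power 0.809 at 30 and 0.876 at 36. The stated 30 is reproduced, and the sample size is not in dispute. It is used below only for the margin 36 − 30 = 6, which 7.1 does not call a dropout allowance.

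**Completion under two denominators.** Let N = 36 dosed per arm (the planned number; 3.1 has all enrolled subjects dosed on Day 1). Let *e* be the stops before meeting 7.3, *l* the later stops, and *c* = N − e − l the completers. The documents give neither *e* nor *l*, so both are assumed.

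- All dosed: c / N
- 7.3 set: c / (N − e)
- Overstatement: c·e / [N(N − e)], which is zero when e = 0

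*First illustration, l = 3:*

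| Early stops | 7.3 set | All dosed | Overstatement (points) |
|---|---|---|---|
| 2 | 31/34 = 91.2% | 31/36 = 86.1% | 5.1 |
| 4 | 29/32 = 90.6% | 29/36 = 80.6% | 10.1 |
| 6 | 27/30 = 90.0% | 27/36 = 75.0% | 15.0 |

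From 2 to 6 early stops, completion of all dosed falls 11.1 points, while the 7.3 figure falls 1.2.

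*Gap between arms (vehicle minus active):*

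| Early active / vehicle | Later active / vehicle | Gap, 7.3 set | Gap, all dosed |
|---|---|---|---|
| 2 / 1 | 3 / 3 | 32/35 − 31/34 = 0.3 | 32/36 − 31/36 = 2.8 |
| 2 / 0 | 3 / 3 | 33/36 − 31/34 = 0.5 | 33/36 − 31/36 = 5.6 |
| 6 / 0 (extreme) | 3 / 3 | 33/36 − 27/30 = 1.7 | 33/36 − 27/36 = 16.7 |
| 2 / 2 | 6 / 3 | 31/34 − 28/34 = 8.8 | 31/36 − 28/36 = 8.3 |

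The last row shows that 7.3 does not hide an imbalance arising only after week 2.

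*Second illustration, total stops fixed at 6 per arm:* completion of all dosed is always 30/36 = 83.3%. The 7.3 set gives 30/35 = 85.7%, 30/34 = 88.2%, 30/33 = 90.9% or 30/30 = 100% when 1, 2, 3 or all 6 stops are early. The overstatement is 2.4, 4.9, 7.6 or 16.7 points.

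**Efficacy.** After baseline, staining is done only at week 8 (6.5.6), and it is not among the week-10 procedures (6.5.7) requested at withdrawal. Early leavers therefore have no post-baseline staining in any set, and no size is claimed for efficacy bias.

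**The case against.** The strongest reply is that the two sections can be read together: 7.2 says how subjects are grouped and 7.3 says who is included, which amounts to a modified intent-to-treat set. The documents do not use that label. More to the point, a set conditioned on two weeks of treatment and a visit still departs from the unqualified principle in 7.2. The reply softens the contradiction without removing it.

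Second, completion is a safety endpoint, 7.2 sends safety variables to the safety population, and 8.5.3 covers all exposed subjects, so the natural denominator may be everyone dosed. That is a fair reading, and it is why the 7.3 percentages are conditional. But 8.5.3 governs adverse-event evaluation only, and the one explicit membership rule points the other way.

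Third, the sizes rest on assumed early stops and vanish if there are none. This stands. The larger figures need most or all stops to be early, or a one-sided imbalance.

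Fourth, restoring all randomised subjects increases missing week-8 staining, and 7.2 imputes only below 25%. With 6 early and 3 later stops, 9/36 = 25.0% of an arm is missing, against 3/30 = 10% under 7.3. If the limit is counted by arm, imputation would not apply. This is a real dependency, but it arises from a separate rule in 7.2 and bites only in the extreme case; 6 stops give 6/36 = 16.7%.

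Fifth, early leavers contribute little to a VAS change: a Day 1 rating and perhaps one unscheduled rating. The Day 1 rating can enter the planned mixed model. How the withdrawal rating maps to a visit is not stated.

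**Conclusion.** The concern holds. Section 7.3 is wrong as written beside 7.2, rather than merely short of detail, and the primary safety endpoint has no defined denominator. The contradiction is textual and needs no assumption. The numerical effect on completion depends on 7.3 being used as the denominator and on how many subjects stop before two weeks. In the illustrations the overstatement runs from 2.4 to 16.7 points. A between-arm gap produced by early stopping is mostly lost, while one produced by later stopping is not. Because the choice of denominator can move a primary endpoint this far, it must be fixed in the plan before unblinding; left open, it could be chosen with the results in view.

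**What to change.** Amend 7.2 and 7.3, with one sentence in 8.1:

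- **Efficacy set:** all randomised subjects, analysed as randomised, with missing week-8 staining handled by the multiple imputation already planned.
- **Safety and tolerability set:** all subjects with at least one dose, analysed as treated. Name it as the denominator for eight-week completion, counting anyone who stops before week 8 as a non-completer, and as the set for the VAS endpoint in 3.2. Say how a withdrawal VAS rating is assigned to a visit.
- **Replacement:** subjects replaced after an adverse-event withdrawal stay in both sets.
- **Supportive set:** keep the present 7.3 population only as a labelled supportive analysis.

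No new visits, data or subjects are needed. The price is that the reported completion rate may be lower, by 5.1 to 15.0 points in the first illustration and 2.4 to 16.7 in the second. Restored early withdrawers will mostly need imputed week-8 staining, so the efficacy gain rests on the imputation model. How the 25% missing-data limit in 7.2 is counted is a separate point and is left unchanged here.
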